3.2.1.3 Handling of Missing or Replicated Data, Unscheduled Visits, and Early Termination Visits

Composite score: NIS score, +7 score, NIS+7 score, modified +7 score, or mNIS+7 score

Missing data imputation strategies for missing visit level data

If a patient misses a visit (or the visit is performed outside the analysis visit window), or the entire mNIS+7/NIS+7 assessment is not conducted at a visit, then the mNIS+7/NIS+7 and the composite, components and subcomponents will be considered to be missing at that visit. In a Mixed Model for Repeated Measures (MMRM), missing data are not explicitly imputed. Instead, all available post-baseline assessments (within the scheduled visit windows) of the endpoint during the treatment period are utilized and via modelling of the within subject correlation structure, the endpoint treatment differences (which are adjusted to take account of missing data) are derived. In addition several 'Missing not at random' methods are described in Section 3.3.3.2 of the statistical analysis plan which will be used as sensitivity analyses to impute missing visit level data.

Missing data imputation strategies for missing assessment level data

Two independent assessments of the primary efficacy endpoint, mNIS+7, are planned at the baseline visit and the Week 66 visit, and the early termination visit (for patients that terminate treatment early). A single mNIS+7 assessment is also planned at the Week 35 visit. The mean of the two replicate assessments within visit will be used for analysis of both the baseline and Week 66 visits (provided both visits fall in the visit window and are within 52 days of the last dose of medication). Subcomponent scores will be averaged first. These will be referred to as the averaged subcomponent scores.

At baseline and Week 66, in the event that only one subcomponent has been performed, the single subcomponent will be used in place of the mean value for that visit for the averaged subcomponent score. If both of the subcomponent values are missing, the averaged subcomponent score is missing. At Week 35, only one assessment is performed, therefore the single subcomponent will be used as the averaged subcomponent score for that visit. These values will be used in the summary and analysis of averaged subcomponent scores.

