Two independent assessments of mNIS+7 are planned at early termination visits. If both assessments are within the same visit window the mean of the two will be used. At early terminations, in the event that only one subcomponent has been performed, the single subcomponent will be used in place of the mean value for that visit for the averaged subcomponent score.

The component scores will be computed by summing the averaged subcomponent scores and the composite scores will be computed by summing the component scores.

Imputation of missing averaged subcomponents

If a patient has completed at least part of the mNIS+7/NIS+7 at a visit then the following imputation method will be used to impute this missing assessment level data for the purposes of determining component scores for summary and analysis.

The following missing data imputation steps will be considered and will be used as described below for Groups A, B, and C:

- Step 1: If at least 50% of averaged subcomponent scores within a component are available, the missing averaged subcomponent scores will be set to equal to the mean of the patient’s other non-missing averaged subcomponent scores in that component. The component score is then calculated.
- Step 2 (baseline): In the unlikely event that there are more than 50% of the averaged subcomponents scores within a component that are missing at baseline, the missing averaged subcomponent scores will be set to equal to mean baseline averaged subcomponent score from the parent study Randomized Set (across treatment groups). The component score is then calculated.
- Step 3 (post-baseline visits): For certain components, and only under certain conditions which will be listed below, the missing averaged subcomponent scores at that visit within that component only will be set equal to the mean averaged subcomponent score among the subjects randomized to placebo in the Randomized Set at that visit. The component score is then calculated.

If a post-baseline assessment does not fall into the scheduled analysis windows, there is no obvious visit on which the mean subcomponent scores in the placebo group can be derived. In order to apply step 3, the following visits will be used to derive the mean scores in the placebo group:

Timing of Visit	Imputation rule
Before Week 35	Randomized Set mean at baseline
Between Week 35 and Week 66	Week 35 placebo mean
After Week 66	Week 66 placebo mean

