Note: when imputing missing subcomponents based on placebo mean at a specific visit, the placebo mean is derived from on-treatment assessments only (i.e., those that were done within 52 days of last dose).

The components of the mNIS+7 and NIS+7 are grouped into A, B and C based on the imputation step used, as follows. A detailed list of components by group can be found in Table 1– Table 3 in Appendix 1:

- Group A: For components with multiple subcomponents except the NCT component of +7, imputation steps 1 and 2 will be applied.

If, after applying step 1 for post-baseline visits, 6 out of the 7 components of the mNIS+7 composite score (NIS-C, NIS-R, NIS-S, NIS-W, HP, TP or NCT) are available and only one is missing at that visit, then step 3 will be applied for the missing component.

If, after applying step 1 for post-baseline visits, 4 out of the 5 components of the NIS+7 composite score (NIS-C, NIS-R, NIS-S, NIS-W, or NCT) are available and only one is missing at that visit, then step 3 will be applied for that the missing component.

Mean averaged subcomponent score used in the imputation described in step 3 are derived from the averaged subcomponent scores before step 1 imputation among the group of patients who were randomized to placebo.

If, after applying steps 1-3 as appropriate, there are still missing subcomponent scores, the component score will be set to missing.

- Group B: For the NCT component of +7, it should be noted that the following 3 of the 5 subcomponents of this component may be “not evaluable” as an additional category to missing: 1) fibular nerve motor conduction velocity (PMCVK), 2) fibular nerve distal latency (PMLA), 3) tibial nerve distal latency (TMLA) (see Table 3 in Appendix 1). These nerve conduction attributes are not evaluable when the tibial or fibular nerve amplitude is 0, therefore, these “not evaluable” results are considered informative missing results and a slightly different imputation method is applied here. The following imputation rule will be used for Nerve Conduction Tests component score of +7: The normal deviate score for PMCVK, PMLA and TMLA will be respectively set to 3.72 (the worse response) if the recorded response was classified “not evaluable.” After this, imputation step 1 and 2 will be applied.

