If, after applying step 1 for post-baseline visits, 4 out of the 5 components of the NIS+7 composite score (NIS-C, NIS-R, NIS-S, NIS-W, or NCT) are available and only one is missing at that visit, then step 3 will be applied for that the missing component.

Mean averaged subcomponent score used in the imputation described in step 3 are derived from the averaged subcomponent scores before step 1 imputation among the group of patients who were randomized to placebo in the Randomized Set at that visit.

Note that these components are *not* used in the nerve conduction component of the *modified* +7, therefore Group B only includes the NCT component of the NIS+7 and not the NCT component of the mNIS+7.

- Group C: The two components, HRDB and vibration tests, have only one subcomponent. Missing data for these averaged subcomponents score will be imputed as follows:
 - For baseline, the missing averaged subcomponent scores will be set to equal to the mean baseline averaged subcomponent score from the Randomized Set (across treatment groups).
 - For post-baseline visits, the missing averaged subcomponent scores at that visit will be set equal to the mean averaged subcomponent score among the subjects randomized to placebo in the Randomized Set at that visit. If a post-baseline assessment does not fall into the scheduled analysis windows, there is no obvious visit on which the mean subcomponent scores in the placebo group can be derived. In order to derive the mean scores in the placebo group, the following visits will be used:

Timing of Visit	Imputation rule
Before Week 35	Randomized Set mean at baseline
Between Week 35 and Week 66	Week 35 placebo mean
After Week 66	Week 66 placebo mean

Composite Score

The composite scores of mNIS+7, NIS+7, modified +7, +7, and NIS will each be calculated by summing the imputed component scores. If any of the component scores after imputation are still missing within a composite, the composite score will be set as missing.

Norfolk QOL-DN Domain and Total score

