3.3.2 Primary Efficacy Analysis

The two primary endpoints, the mNIS+7 and the Norfolk QOL-DN questionnaire total score, will be tested using a ranking strategy with the mNIS+7 tested first and the Norfolk QOL-DN tested second. The primary efficacy analyses will be the contrast between the ISIS 420915 300 mg group and the placebo group at Week 66 from a Mixed Effects Model with Repeated Measures (MMRM) of change from baseline in each of these two endpoints during the treatment period. The primary analysis will be conducted using the Full Analysis Set (FAS). Interpretation will be made in a stepwise approach; should the null hypothesis, based on the mNIS+7, be rejected at a 2-sided 0.05 significance level, then the Norfolk QOL-DN questionnaire total score will be tested. However, if the null hypothesis for the mNIS+7 is not rejected, testing for the Norfolk QOL-DN questionnaire total score will be considered exploratory. No adjustment is therefore required for multiple hypothesis testing. This sequential testing procedure for the two primary objectives controls the overall Type I error rate at a 2-sided 0.05 level and is based on the methodology developed in Dmitrienko, Tamhane and Wiens (2008). The primary study hypotheses will be formally evaluated at the time of the end of treatment lock, occurring after all patients have completed the EOT assessments, the database is locked and treatment code is unblinded.

The MMRM method will include fixed categorical effects for treatment (two levels), time (two levels), treatment-by-time interaction, and each of the 3 randomization stratification factors (each with two levels). The baseline value of the endpoint and the baseline-by-time interaction will be included as fixed covariates in the model. Model parameters and treatment effects could be estimated by the following example SAS code:

CCI

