3.3.3 Additional Analyses of Primary Endpoints

In addition to the primary efficacy analysis, the following sensitivity analyses will be conducted on the FAS except where noted for each of the two primary efficacy endpoints:

- **Sensitivity Analysis 1 (Non-Parametric Analysis)** – The non-parametric Van-Elteren test will also be performed for the two primary study endpoints as the sensitivity analysis. Hodges-Lehmann estimates of the differences between ISIS 420915 300 mg group and the placebo group as well as distribution-free CIs based on the Wilcoxon Rank Sum Test will also be provided.
- **Sensitivity Analysis 2 (Conservative Assessment Level Imputation)** – To examine whether the primary analysis results are robust to the strategy for imputing missing assessment level data, an alternative strategy that results in a conservative estimate of the treatment effect will be implemented. Patients without an assessment at a visit will not have their score imputed for that visit. Imputation of missing baseline assessment level data will follow the approach detailed in Section 3.2.1.3. For patients with at least one non-missing post-baseline subcomponent score missing data will be imputed as follows. Missing post-baseline assessment level data will be imputed for the placebo group using their observed or imputed baseline value. Missing post-baseline assessment level data will be imputed for the ISIS 420915 group using the placebo mean in the Randomized population for that subcomponent at that visit (done after the placebo imputation).
- **Sensitivity Analysis 3 (Excluding Assessments done at Early Termination Visits)** – In order to examine the robustness of the primary analysis to the inclusion of premature termination data, the primary efficacy analysis will be repeated excluding data collected at early termination visits which are included in the primary analysis.
- Sensitivity analyses will be performed to investigate the impact of alternative missing data assumptions (see sections 3.3.3.2 and 3.3.3.3). These analyses will be done on the Safety Set and will be labeled as:
 - **Sensitivity Analysis 4** – Multiple Imputation assuming Missing at Random
 - **Sensitivity Analysis 5** – Multiple Imputation assuming Copy Increments from Reference
 - **Sensitivity Analysis 6** – Multiple Imputation assuming Jump to Reference
 - **Sensitivity Analysis 7** – Data at Withdrawal Visit Included

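### The placebo-mean fill for a missing mNIS+7 component ignores the patient's own baseline, so Sensitivity Analysis 2 is not assured to be conservative

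*SAP*

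**What the plan says.** SAP 3.2.1.3 deals with partly completed mNIS+7 assessments in steps. Step 1 fills gaps from the patient's own remaining sub-scores when at least half of a component's sub-scores are present. Step 3 covers what is left after baseline. It fills "the missing averaged subcomponent scores at that visit within that component only", and each such score "will be set equal to the mean averaged subcomponent score among the subjects randomized to placebo in the Randomized Set at that visit". The placebo mean comes from on-treatment assessments only, and the rule applies in both arms. The Group A text limits its use: six of the seven multi-part components must be present, that is, they "are available and only one is missing at that visit, then step 3 will be applied for the missing component". Group C treats heart rate to deep breathing (HRDB) alike, without that condition: a missing value is "set equal to the mean averaged subcomponent score among the subjects randomized to placebo".

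The endpoint is change from baseline in the summed score (SAP 3.3.1). The only baseline adjustment in SAP 3.3.2 is for the composite: "The baseline value of the endpoint and the baseline-by-time interaction will be included as fixed covariates in the model".

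For Sensitivity Analysis 2 (SAP 3.3.3) the plan says "an alternative strategy that results in a conservative estimate of the treatment effect will be implemented". Missing post-baseline sub-scores of placebo patients take their own baseline value. Those of active patients take the placebo mean for that sub-score and visit, computed after the placebo fill. The text mentions neither Step 1 nor the six-of-seven condition.

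**The concern.** A placebo mean is a sensible reference for an active patient with missing data. The difficulty is that it is an absolute score. Subtracting the patient's own baseline credits someone who started worse than average with improvement that nobody observed, and charges someone who started better with decline. The composite-baseline covariate does not remove this: a component baseline is only partly predicted by the composite, and the error falls only on imputed patients. In simulation, the adjusted and unadjusted biases differed by no more than about 0.1 point.

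In the primary analysis the errors cancel between arms if the share imputed times the excess baseline severity is the same in both. In Sensitivity Analysis 2 they cannot cancel, because only the active arm receives the absolute mean. A check meant to lean against the drug could then lean towards it. No listed analysis uses own baseline plus placebo change. Sensitivity Analyses 4 to 6 concern missing visits, not missing components.

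**Working it through.** **Plan's own figure.** SAP section 4 assumes 135 patients at 2:1, 25% dropout, difference 9.6 and SD 14. That leaves 33.75 and 67.5 patients. SE = 14 x sqrt(1/33.75 + 1/67.5) = 2.95; 9.6/2.95 = 3.25; power = Phi(3.25 - 1.96) = 90.2% (89.7% by noncentral t with 34 and 67). The stated 90% is reproduced.

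**Inputs not in the documents (assumptions).** One component has baseline SD 10 and carries a quarter of the change. From SAP section 4, placebo change in it is 16/4 = 4.0, active change 6.4/4 = 1.6, and the difference 2.4. The log-odds of being missing rise by 1 per SD of component baseline. Numerical integration then gives the excess baseline d of missing patients: 9.5 points at 2% missing, 9.3 at 3%, 9.0 at 5%, 8.2 at 10% and 7.5 at 15%. The SD is plausible only by inference. The +7 maximum of 26.04 equals 7 x 3.72, and 102.32 - 6 x 3.72 = 80.00, which suggests that the two sensory components share 80 points. The scoring tables are redacted.

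**Primary analysis.** With p the share imputed,

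bias = p_active x (placebo minus active component change) - (p_active x d_active - p_placebo x d_placebo).

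A negative value favours the drug. The first term is the intended shrinkage towards placebo; the second is the baseline-severity error.

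| Active / placebo missing | First term | Second term | Net, planned effect | No effect |
|---|---|---|---|---|
| 10% / 10% | 0.10 x 2.4 = +0.24 | 0 | +0.24 | 0 |
| 5% / 2% | +0.12 | -(0.45 - 0.19) = -0.26 | -0.14 | -0.26 |
| 15% / 3% | +0.36 | -(1.13 - 0.28) = -0.85 | -0.49 | -0.85 |
| 3% / 15% | +0.07 | -(0.28 - 1.13) = +0.85 | +0.92 | +0.85 |

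A simulated Week 66 ANCOVA (67 and 34 patients) under no effect gave -0.27 at 5%/2% without type I inflation, and -0.88 at 15%/3% with 5.3% rejection. With own baseline plus placebo change the bias was -0.02 to 0.00.

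**Precision.** With 10% imputed in each arm, unrelated to severity, and the whole component missing, power was 86.6% under the SAP rule and 88.2% under the increment rule. With 4 of 10 sub-scores observed it was 88.2% and 88.8%.

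**Sensitivity Analysis 2, 10% missing in each arm, planned effect.**
- After the placebo fill, the placebo mean change is 4.0 x 0.9 = 3.6.
- Active error: 0.10 x (3.6 - 1.6 - 8.2) = -0.62.
- Placebo patients are given zero change, so the placebo mean falls by 0.10 x 4.0 = 0.40, which adds +0.40 to the difference.
- Estimate: -9.6 - 0.62 + 0.40 = -9.82. The primary analysis gives -9.6 + 0.24 = -9.36.
- With the increment rule in the active arm: -9.6 + 0.10 x (3.6 - 1.6) + 0.40 = -9.00.

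Simulation gave -9.82, -9.37 and about -9.0. With 4 of 10 sub-scores observed, Sensitivity Analysis 2 gave -9.74 and the primary analysis -9.46. On these inputs Sensitivity Analysis 2 shows a larger effect than the primary analysis once d exceeds 3.6 points (0.2 - 0.1d + 0.4 < 0.24), and a larger effect than the truth once d exceeds 6.0 (0.2 - 0.1d + 0.4 < 0).

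**The case against.** The strongest reply concerns frequency. To reach Step 3 at Week 66, a component must stay mostly missing after two assessments on separate days, the single-replicate rule and Step 1, and it must be the only one missing. Visits outside the window do not reach the model, since a visit counts as missing if it is absent "or the visit is performed outside the analysis visit window". The trial is double-blind with an insulated NIS evaluator, and no document supports a fivefold difference between arms. All of this stands. It is why the primary-analysis bias is probably small, and it is small beside an SE near 3.

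Five stronger readings are tempting but not supported:

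- **The SAP itself concedes informative missingness.** It says certain "results are considered informative missing results and a slightly different imputation method is applied here", but this concerns three nerve-conduction attributes of the +7. The SAP states that they are not used in the modified +7, and they have their own worst-score rule.
- **The modified +7 data were known to be incomplete.** The DSMB SAP (1.2) says so of interim data. Its section 3.2.1 explains that results were withheld from entry until queries were resolved, so this is largely entry lag.
- **The rule favours the drug.** The sign depends on which arm has more missing data and on whether those patients started worse or better.
- **HRDB adds materially.** Its inferred span is about 3.72 points, its effect is negligible, and Sensitivity Analysis 12 removes it.
- **Much larger components are realistic.** An SD of 20 on an inferred 40-point scale would need every patient at one end or the other.

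**Conclusion.** The rule is as described and worth changing, but as a conditional point. Balanced missingness costs mainly a little power. Severity-related and unequal missingness moves the primary estimate by about -0.1 point (5% versus 2%) to -0.5 point (15% versus 3%) under the planned effect, and by about -0.3 to -0.9 under no effect. The direction reverses if placebo has more gaps. These sizes rest on an assumed component SD of 10, a quarter of the change in that component, and assumed missingness rates.

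The firmer conclusion concerns Sensitivity Analysis 2. Its conservative label is not assured by its construction, even with equal missingness, if missing patients started worse: about -9.8 against -9.4 for the primary analysis. If they started better than average, the error runs the other way.

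A reader might infer that imputing increments cures the missing-data problem. It removes only the part tied to baseline severity. Where missingness tracks progression instead (15% versus 3%, SD 10), both rules gave a bias of about -0.30.

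**What to change.** Before unblinding, while the SAP can still be finalised (SAP 2.6):

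1. In the active arm of Sensitivity Analysis 2, impute the patient's own baseline sub-score plus the mean placebo change in that sub-score at that visit, bounded to the sub-score's scale. Keep the current mean where the baseline sub-score was itself imputed.
2. Use the same rule in Step 3 for in-window visits. If the primary scoring rule is kept, add this version as a sensitivity analysis. Step 2, the out-of-window table and the HRDB rule can stay.
3. Tabulate Step 3 imputations by component, visit and arm, with the mean baseline of the filled sub-scores in imputed and other patients, so that the bias formula can be evaluated on real figures.

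The idea is already in the SAP: Copy Increment from Reference (3.3.3.2) uses placebo increments for missing visits. The cost is a little wording and programming, no new data, and some truncation at scale limits. In a check bounded to 0-40 points (SD 10, 10% imputed), the estimate was -9.18 under both rules and power was 86.1% with the SAP rule against 87.4% with the bounded increment.

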3.2.1.4 Data Summary Plan

The table below details what data will be included in the summary and analysis output by endpoint type, and what output is planned for the EOT and what output will be updated for the EOS. Data summarized/analyzed at EOT will be based on data collected up to the date of the data cut. It is possible that the on-treatment set of data available at EOS will be different to the one that was available at EOT because data collected after the EOT data cut may slot into the on-treatment period. On-treatment output provided at the EOT will be updated at EOS if the data in the on-treatment period has changed from EOT. In select instances the data for a type of endpoint that is summarized or analyzed may not be consistent with the rules in the Table; such exceptions will be noted in this document. Note: assessments for mNIS+7, NSC, ERG, and ophthalmology done early in the treatment period that are used for baseline cannot also be used as an on-treatment assessment.

Endpoint type	Provide at EOT	Update at EOS	Comment/definition
Efficacy	-Listings -On-treatment summary/analysis tables -Post-treatment summary tables	-Listings -On-treatment summary/analysis tables -Post-treatment summary tables	-On-treatment: First dose date \leq Date of assessment \leq Last dose date + 52 days -Post-treatment: Date of assessment $>$ last dose date + 52 days -Visit defined by analysis visit window -The primary inference for mNIS+7 and Norfolk QOL-DN will be made at EOT, even if data slotted in the on-treatment period has changed by EOS
PD, BMI and mBMI, ERG	-Listings -On-treatment summary/analysis tables -Post-treatment summary tables	-Listings -On-treatment summary/analysis tables -Post-treatment summary tables	-On-treatment: First dose date \leq Date of assessment \leq Last dose date + 28 days -Post-treatment: Date of assessment $>$ last dose date + 28 days -Visit defined by analysis visit window
ECG, Lab, vital signs (including body weight),	-Listings -On-treatment summary tables -Post-treatment summary tables	-Listings -On-treatment summary tables -Post-treatment summary tables	-On-treatment: First dose date \leq Date of assessment \leq Last dose date + 7 days -Post-treatment: Date of assessment $>$ last dose date + 7 days -Visit defined by analysis visit window -Abnormal lab analyses described in Sections 3.9.4.1 to 3.9.4.3 include post-baseline data

Endpoint type	Provide at EOT	Update at EOS	Comment/definition
			collected up to the day of the patient's last contact date within the study
AE	-Listings -On-treatment summary tables -On-study summary tables	-Listings -On-treatment summary tables -On-study summary tables	-On-treatment summary tables include TEAE with onset dates up to the last dose date + 7 days -On-study summary tables includes all TEAE in the study, including those with onset dates > 7 days after last dose
Concomitant/ Prior medications	-Listings -On-treatment summary tables -On-study summary table	-Listings -On-treatment summary tables -On-study summary table	-On-treatment summary tables include medications taken on or after the study drug first dose date and up to the study drug last dose date +7 days - On study summary tables include medications taken after the study drug first dose date - Medications taken before the first dose date will be considered prior.
Immunogenicity	-Listings -On-study summary/ analysis tables	-Listings -On-study summary/ analysis tables	-On-study summary/analysis tables include post-baseline data collected up to the day of the patient's last contact date within the study -Visit defined by analysis visit window
PK	-Listings -On-study summary/ analysis tables	-Listings -On-study summary/ analysis tables	-Summary/analysis tables include post-baseline data collected include data collected up to the day of the patient's last contact date within the study -PK parameters will be derived based data collected up to the patient's last contact date within the study -PK concentration will be summarized based on nominal scheduled visits -All PK parameters will be recalculated using all available data at EOS

